*We will also examine the feasibility of using electronic health record (EHR) data as an additional measure of health, pain, and cognitive outcomes.*

To visually examine these hypotheses (as significance testing is not appropriate for a pilot study), we will extract data on clinical outcomes from the EHR to examine patient outcomes before and after engaging in the intervention and to compare group differences.

We expect that patients in the KNA condition will have higher rates of transferring to MCI or normal range on the RBANS and improvements in functional status on the FSQ. Participants in the KNA condition will have reductions in self-reported pain and greater improvements on other health indices. Additionally, we expect higher rates of measurable ketones (trace or higher) in the KNA program compared to KN-only based on daily, at-home urinalysis test strips. Combined, these data will provide important information about the clinical effects of the programs and feasibility of the proposed study components for a larger ePCT.

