Screening phone call. After confirming interest in being contacted about the study, participants will be contacted by a member of the research team and screened for eligibility. This screening will include a telephone MoCA, sections 1 and 4 from the Functional Status Questionnaire, a brief memory complaint scale, a brief self-rated pain during the past week (0-10), and self-reported height, weight, and age. Participants will also be asked to report any restrictive dietary or medical conditions that may make them unable to change their nutrition. Participants will be compensated with a \$5 e-gift card for completing the screening and will be asked to provide their full name and email address to receive the gift card. This contact information will not be retained for future research purposes unless participants consent to be contacted for future studies. All screened participants will be provided with a handout on healthy living designed in collaboration with the SeniorHealth physicians. If participants are eligible, then they will be sent an online consent form via REDCap, which they will read and review using HIPPA-compliant Zoom with a member of the research team before signing. The study team will then complete a final eligibility check of the patient's EHR, self-reported health conditions, or provided health records and review with a SeniorHealth physician to confirm eligibility and ensure participant's safety. The SeniorHealth physician will be blinded to participant identify of non-clinic participants. Participants who are eligible and consent to participate will have screening data linked with other study data, in order to reduce redundancy in assessment measures.

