Baseline Assessment (Time 1). In addition to embedded EHR and other health record data, we are collecting additional data to evaluate the personal impacts of the intervention. This in-person assessment will include: the Repeatable Battery of Neuropsychological Status (RBANS update – form A), GAS, PHQ-9, FSQ, ISEL, MSQ, CAIDE risk score, OPQOL, GSE, PSQI, SCOFF, social support, self-efficacy, a verbal pain descriptor scale, the Brief Pain Inventory, The WOMAC-Pain scale, the PANAS, PSS, the WHY-MPI, and the Roland-Morris Pain and Pain-related Disability scale, a fasting blood draw for a comprehensive metabolic panel and HbA1C (completed by a certified medical assistant), a weight and body composition assessment, and basic vitals (blood pressure and heart rate). Participants will be scheduled in the morning for these assessments in order to allow approximately 10-hour fasting for the blood draw. This assessment will be completed in-person following COVID-19 precautions (described in section 14), and patient participants will be compensated \$30 for their time.

Post-intervention Assessment (Time 2). Participants will complete this assessment in the final weeks of the program, in order to assess participants when they are in ketosis. Participants will be asked to return their ketone logs either electronically, reported over the phone, or via mail to the study PI. The research team will complete qualitative interviews with participants to collect information about barriers and facilitators to completing the program and adhering to KN. Participants will complete the RBANS update – Form B, the PHQ-9, FSQ, MSQ, GAS, CAIDE risk score, OPQOL, PSS, PSQI, social support (ISEL), self-efficacy (GSE), group cohesion, a verbal pain descriptor scale, the Brief Pain Inventory, The WOMAC-Pain scale, the PANAS, the Roland-Morris Pain and Pain-related Disability scale, the WHY-MPI, and participants' global impression of change, a second fasting blood draw for comprehensive panels (completed by a certified medical assistant), a weight and body composition assessment, and basic vitals (blood pressure and heart rate). Participants will be scheduled in the morning for these assessments in order to allow approximately 10-hour fasting for the blood draw. This assessment will be completed in-person following COVID-19 precautions, and patient participants will be compensated \$30 for their time.

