### Inclusion Criteria

To meet eligibility for inclusion in the intervention, participants must be 60-85, meet criteria for possible mild cognitive impairment, have a Telephone MoCA score >12, be English speaking, and have internet access with video conferencing, and report interest in participating in a nutrition intervention. In addition to the criteria above, a subsample of 20 participants will be selected based on self-reported pain on the Rolland-Morris pain scale (A1) of 3 or greater during the past week.

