### Exclusion Criteria

Participants will be excluded if they report any exclusionary health or major psychiatric conditions as determined by their physician at the FSU SeniorHealth clinic (e.g., Type 1 diabetes, schizophrenia etc.), are under-weight based on BMI, have a diagnosable major neurocognitive disorder, or if they report use of prescriptions that may interact with their ability to adhere to the diet (e.g., insulin, MAOIs, immunosuppressant etc.). Those deemed unable to provide informed consent based on the telephone cognitive screener (MoCA<12) will be excluded.

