### **15.0 Potential Benefits to Subjects\***

A goal of the current study is to assess whether ketogenic nutrition may be beneficial for memory and pain severity in older adults and whether the use of an MI-CBT group approach may improve adherence to this type of nutrition. Previous research has demonstrated that a low-carbohydrate diet has multiple benefits on cognitive functioning, pain, and other health factors in older individuals. Thus, participants will be provided with a supportive environment for making this diet change as well as empirically validated cognitive behavioral skills for behavior change in general.

During the proof-of-concept preliminary trial, participants reported improvements in energy stability, alertness, blood glucose levels, and mood. Participants may experience improvements in their cognitive status and will be closely monitored by health professionals.

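### Ketones measure adherence in both objectives, yet no ketone or diet reading precedes the program, and people already eating ketogenically or from the earlier trial are not identified.

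*Protocol*

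**What the plan says.** **Endpoint.** Protocol Section 2.0 uses ketones twice. Objective 1 compares ketone levels between arms at week 6. Objective 2 adds that "we expect higher rates of measurable ketones (trace or higher) in the KNA program compared to KN-only", and Section 4.0 repeats this. Section 2.0 also says that the groups will be examined visually, without significance tests.

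**Eligibility.** Section 9.0 (Inclusion Criteria) requires that participants "have internet access with video conferencing, and report interest in participating in a nutrition intervention", along with age, cognition and language conditions. The Exclusion Criteria come closest to diet where they remove people "if they report use of prescriptions that may interact with their ability to adhere to the diet". Neither list mentions current ketogenic eating or participation in an earlier KN study. Such a study existed: Section 15.0 states "During the proof-of-concept preliminary trial, participants reported improvements in energy stability", and Section 5.0 (KNA Weeks 2-4) refers to feedback from a feasibility trial.

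**Screening.** Section 6.0 (Screening phone call) and Section 12.0 (Preliminary screen) ask people to "report any restrictive dietary or medical conditions that may make them unable to change their nutrition".

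**Before the program.** Time 0 in Section 6.0 collects diagnoses, medications, vitals and laboratory values. Time 1 is a long list of scales plus vital signs and "a fasting blood draw for a comprehensive metabolic panel and HbA1C (completed by a certified medical assistant), a weight and body composition assessment". Neither contains a ketone test, food log or diet recall.

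**During the program.** Food logs start with the week 1 session (Section 5.0), and ketone levels are reported in the weekly survey of the active phase (Section 6.0, Weekly Assessments). Time 2 is placed in the final weeks so that participants are seen while in ketosis.

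**The concern.** Someone already in ketosis would count as adherent in either arm whatever the program does, and would have little diet change left through which cognition, pain or HbA1c could improve. Someone from the earlier trial who is assigned to KN-only could bring its skills into the comparison arm. The protocol neither excludes nor flags either kind of person.

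The threshold for a positive strip is low (trace or above), and its background rate in this population is unknown without a reading before the program. At 20 to 30 per arm, compared by eye, a chance imbalance in already-ketogenic people could pass as signal or hide it. The timing of Time 2 also means that the pre/post contrast takes participants to be out of ketosis at Time 1, and nothing checks this.

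The statistical analysis plan is not at hand, but it could not repair this. Eligibility and the visit schedule are set in the protocol, and no analysis recovers a reading that was never taken.

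**Working it through.** The protocol gives no effect size, power or expected ketone rate, so there is no stated figure to reproduce. The check has two parts.

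**1. Is there any reading or flag before the program?** Sections 6.0 (screening call, Time 0, Time 1), 9.0 and 12.0 contain none. The screening question concerns inability to change diet, and a person already on the diet can truthfully report none. Remote Time 3 visits collect a ketone test where one is available, so a single reading is treated as practical at follow-up but is not asked for at baseline.

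**2. How much could a chance imbalance matter?**

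Inputs from the protocol: 30 per arm (Section 12.0), and a minimum of 40 in total (Section 11.0), taken here as 20 per arm.

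Assumptions, not in the documents: 60% v 40% positive strips among people new to the diet, already-ketogenic people positive in both arms, and K such people enrolled, with K = 0, 3, 6 or 9.

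Let a of them fall in KNA and b in KN-only, with n per arm. The expected difference is

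D = [a + (n − a)(0.60)]/n − [b + (n − b)(0.40)]/n = 0.20 + 0.40a/n − 0.60b/n.

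*Three people, all in one arm of 30:*
- All in KNA: (3 + 27 × 0.60)/30 − 0.40 = 0.64 − 0.40 = 24 points.
- All in KN-only: 0.60 − (3 + 27 × 0.40)/30 = 0.60 − 0.46 = 14 points.

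*The same at 20 per arm:* 0.20 + 0.40 × 3/20 = 26 points, or 0.20 − 0.60 × 3/20 = 11 points.

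*Chance of such a split* (hypergeometric):
- 30 + 30: 2 × C(30,3)/C(60,3) = 2 × 4,060/34,220 = 0.237.
- 20 + 20: 2 × C(20,3)/C(40,3) = 2 × 1,140/9,880 = 0.231.

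*Other values of K at 30 + 30:*

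| K | Average D | Smallest gap of 3 or more | Chance of that gap or larger | D at that gap |
|---|---|---|---|---|
| 0 | 20 | none | 0 | 20 |
| 3 | 19 | 3 | 0.237 | 24 or 14 |
| 6 | 18 | 4 | 0.195 | 24.7 or 11.3 |
| 9 | 17 | 3 | 0.472 | 22 or 12 |

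Average D is 0.20 × (1 − K/60). With six people the gap is always even, so 4 is the smallest gap of 3 or more. This is why the probabilities do not rise steadily with K.

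*For scale:* the sampling standard error of a 60% v 40% difference at 30 per arm is √(2 × 0.24/30) = 0.126, or 12.6 points.

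**The case against.** The strongest reply is that the ketone hypotheses compare randomised arms and are not changes from baseline. This stands. A reader might infer that the week-6 comparison is biased or invalid without a baseline reading. The protocol does not support that, because background ketosis is balanced in expectation. The harm is loss of information, not bias.

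The effect is also modest. A reader might take a three-person gap to be worth 3/30 = 10 points. That treats each such person as an extra positive, although many would have been positive anyway. Under the assumed rates the shift is +4 or −6 points, and average dilution is 1 to 3 points, against a standard error of 12.6.

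Prevalence is conjecture, and zero is possible. Low-carbohydrate eating is not ketosis: Section 5.0 treats 125 g and 75 g of net carbohydrate as early steps. A reader might also infer that earlier participants will re-enrol, because recruitment uses people who agreed to research contact. The documents do not say that the two groups overlap.

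Partial safeguards exist. A ketogenic eater might mention the diet when asked about restrictive dietary conditions, and early week 1 strips might reveal someone already in ketosis. Neither is reliable. The question has another purpose, and the week 1 readings come after assignment and the opening session, so they may already reflect the program.

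Finally, broad eligibility is a legitimate choice in a pragmatic pilot that already foresees recruitment difficulty. This stands against making exclusion mandatory. It does not count against recording the facts.

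**Conclusion.** The point holds as a cheap improvement to the design. The protocol uses ketones as its adherence measure in both objectives, but takes no ketone or diet reading before the program and does not identify people already eating ketogenically or from the earlier KN trial. The background rate of positive strips is therefore unknown, a chance imbalance could not be reliably seen or adjusted for, and the pre/post contrast rests on an unchecked assumption about Time 1.

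As to size, three already-ketogenic people all in one arm would move an assumed 20-point difference to 24 or 14 points at 30 per arm, or to 26 or 11 at 20 per arm. If three such people enrolled, that split would occur with probability about 0.23 to 0.24. These figures rest on the assumed 60% v 40%, on such people always testing positive, and on their being enrolled at all. The documents do not say that they will be, only that nothing excludes or flags them.

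**What to change.** 1. **Time 1 (Section 6.0).** Add one urine ketone strip reading before any diet change. Report week-6 ketones alongside that reading or adjusted for it.
2. **Screening call (Sections 6.0 and 12.0).** Ask and record two things: whether the person currently follows a ketogenic diet, and whether they took part in the earlier KN trial. Report the ketone comparison with and without those who answer yes. Screening precedes random assignment in Section 12.0, so the restricted comparison is still a randomised one.
3. **Section 9.0.** State how the answers are handled. Whether to exclude such people is the investigator's choice, since exclusion costs some recruitment. If low-carbohydrate eating is to be used as a criterion, it needs a definition.

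The cost is one strip per participant (the protocol does not say who supplies the strips), two short questions and a short amendment. Recording alone costs no recruitment.

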### Exclusion Criteria

Participants will be excluded if they report any exclusionary health or major psychiatric conditions as determined by their physician at the FSU SeniorHealth clinic (e.g., Type 1 diabetes, schizophrenia etc.), are under-weight based on BMI, have a diagnosable major neurocognitive disorder, or if they report use of prescriptions that may interact with their ability to adhere to the diet (e.g., insulin, MAOIs, immunosuppressant etc.). Those deemed unable to provide informed consent based on the telephone cognitive screener (MoCA<12) will be excluded.

## **10.0 Vulnerable Populations\***

Participants, age 60-85, years may enroll in the proposed study. We will not include any participants who are unable to provide consent. Of note, a mild neurocognitive disorder (MNCD) also known as MCI is characterized by slight decline in cognitive functioning, which require compensatory strategies to retain independence. Individuals with MNCD are able to live and function independently and are able to provide consent to participate. The PI is a licensed clinical psychologist with a specialty in geropsychology and will rule out individuals who do not have capacity to consent via a telephone cognitive screener.

Potential harms from participating in this study are not greater than those encountered in everyday life, standard medical care, or during the performance of routine physical or psychological evaluations. Participants will be assured that their information will be kept confidential to the best of the study team's ability, and the responses they provide will have no impact on their relationship with any academic or health institution. The study team will screen potential participants for possible dementia in order to ensure participants have the cognitive capacity to provide consent to participate.

## **11.0 Local Number of Subjects**

We are seeking to enroll a maximum of 60 participants and a minimum of 40 participants.

## **12.0 Recruitment Methods**

Recruitment methods will be employed to engage up to 60 participants (aged 60–85), to participate in this study. Recruitment materials include a study informational flyer (see attached), which will be posted throughout the community at locations that provide permission to post the flyer. The flyer may also be handed out directly to interested individuals. The flyer will contain information about the nutrition program, research, and study team contact information. The research team is available to answer questions about the study including participant responsibilities, benefits, risks, and alternatives.

We will work with our stakeholders/partners at FSU SeniorHealth™ clinic to increase awareness regarding the study. They will receive a study packet, including study summary, a participant study information sheet, and study team contact information. We will ask them to refer the participants to the study and to distribute study information to interested participants. Interested participants will receive a study information sheet and study team contact information which will include a website link to the primary study screener for eligibility determination and subsequent enrollment. They will also be asked to share a link on their website regarding our study.

Additionally, the PI and trained study team members on the project may hand out flyers and collect contact information from interested individuals during community events and community talks. With participants' permission, any contact information collected will be added to a protected online document for participants interested in being contacted about potential research participation and physical copies will be destroyed.

Preliminary screen. After confirming interest in being contacted about the study, participants will be contacted by a member of the research team and screened for eligibility. This screening will include a telephone MoCA, sections 1 and 4 from the Functional Status Questionnaire, a brief memory complaint scale, self-rated pain during the past week (0-10), and self-reported height, weight, and age. Participants will also be asked to report any restrictive dietary or medical conditions that may make them unable to change their nutrition. Participants will be compensated with a \$5 e-gift card for completing the screening and will be asked to provide their full name and email address to receive the gift card. This contact information will not be retained for future research purposes. All screened participants will be provided with a handout on healthy living designed in collaboration with the SeniorHealth physicians. If participants are eligible, then they will be sent an online consent form, which they will read and review using HIPPA-compliant Zoom with a member of the research team before signing. For participants who are patients at FSU SeniorHealth, the study team will then complete a final eligibility check of the patient's EHR and review with the physician to confirm eligibility and ensure participant safety. For participants who are not patients at FSU SeniorHealth, we will request patients provide a copy of their most recent medical records, including health conditions, medications, and recent lab work – this step will be optional. The study team will determine final eligibility of these patients based on self-reported health conditions or review of the records they provide. Participants who are eligible and consent to participate will have screening data linked with other study data, in order to reduce redundancy in assessment measures. Patients and participants who have previously provided consent to be contacted for research may be called or emailed to assess interest in the study if they are not screened during their normal clinic visits. From this sample, we will recruit up to 60 patients who meet criteria for possible MCI (e.g., MoCA score of 18-25 and some self- or other-reported changes in daily living due to cognition). 20 participants will be selected based on self-reported pain of moderate intensity or greater in addition to the other inclusion criteria. There will be two intervention conditions: 30 patients will be randomly assigned to the 6-week KNA group program and 30 to the KN-only condition. All patients will be given the option of signing up for one of three start dates for the programs, with 10 patients maximum in each group. These conditions are designed to determine whether MI- CBT strategies improve adherence to KN, thereby enhancing the benefits compared to providing KN information alone. Key stakeholders in the clinic will be engaged early in the project to increase buy-in to the intervention and to introduce staff to the project.

Recruitment call. The group leaders and study coordinators will call potential participants to provide more information about the respective programs and to determine the patients' interest and availability to participate. A log will be maintained that will track the calls made by the group leaders to provide information regarding the study to prospective participants. The log will include the number of times they were contacted, date they were contacted on, name of the person contacted or spoken to and their initial and final response. Individuals who indicate that they would like to join the study will be provided with detailed study information; additionally, SeniorHealth patients will be asked to provide verbal and electronic written

consent and signed HIPAA authorization. After a final eligibility review of the EHR (for SeniorHealth patients) and self-reported health conditions, participants will then be randomly assigned to a condition.

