Pre-intervention EHR data download & collection of Health Records(Time 0). FSU SeniorHealth patients will be asked to provide our team access to relevant EHR data. Participants who are not patients at FSU SeniorHealth will be asked to provide the same records if possible, but self-reported health conditions and medications will be accepted. Our team will extract and clean relevant EHR/health data on participants who consent to participate in the study. Data from EHR/health records will be used to conduct a secondary eligibility screening to determine if there are any other major health conditions that will exclude participants from the study. Data requested will only include the minimum PHI necessary to complete the proposed study. Data from the EHR or requested health records will include the following information only from appointments pertinent to the study: patients' problem/diagnostic list, medication list, patient vitals, metabolic panels, HbA1C, potassium, CRP, scores on recent cognitive and psychological assessments (i.e., MoCA, depression inventories), and relevant provider notes about a patient's cognitive functioning and pain. Data from the EHR/health records will be used to calculate a CAIDE dementia risk score (Exalto et al., 2014), which includes age, education, sex, cholesterol, BMI, and systolic blood pressure (See Figure 1). The FSU SeniorHealth EHR is maintained on Athena and thus all the information will be accessed from Athena by the study PI, who is a licensed clinician who has completed the required HIPAA and Privacy trainings required to access this information. These data will include the participants MoCA scores, GDS, and FSQ scores or relevant qualitative data about their activities of daily living, and demographic characteristics. We will also include laboratory results that may be relevant to cognitive outcomes for secondary data analyses, including: HbA1c, glucose, potassium,

blood pressure, and cholesterol. Laboratory data that is pulled from the EHR, will be used as a comparison to metabolic and HbA1c data obtained from a blood draw during two in-person assessments.

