## **8.0 Study Timelines\***

See table below.

Timeline for proposed research activities		1	2	3	4	5	6	7	8	9	10	11	12
Year 1													
Submit IRB application		X											
Refining implementation with key stakeholders			X	X	X								
Cleaning and standardizing the EHR				X	X								
Training workshop for clinic staff					X								
Standardize clinic procedures for screening			X	X	X	X	X	X					
Initial screening and recruitment (build waitlist)							X	X	X	X	X	X	X
Resubmit K23 application										X	X		
Recruitment calls											X		
Year 2		1	2	3	4	5	6	7	8	9	10	11	12
Pre-intervention EHR data extraction (groups 1&2; T0)		X											
Baseline phone assessments: groups 1&2 (T1)			X	X									
Intervention period				X	X								
Post-intervention phone assessments (T2)					X								
Post-intervention EHR data extraction (T3)						X	X	X					
Pre-intervention EHR data extraction (groups 3&4; T0)						X							
Baseline phone assessments: groups 3&4 (T1)						X	X						
Intervention period							X	X					
Post-intervention phone assessments (T2)								X					
Post-intervention EHR data extraction (T3)								X	X	X			
Data cleaning and Manuscript development			X	X	X	X	X	X	X	X			
Develop and submit new NIA application					X	X	X	X	X	X	X		

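### Assignment is triggered by the eligibility review, and Time 1 need not be completed first, so the main Objective 2 baselines can be taken after allocation is known

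*Protocol*

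**What the plan says.** Section 12.0, Recruitment call, fixes the moment of assignment. Once records (for clinic patients) and self-reported conditions have had their last eligibility check, "participants will then be randomly assigned to a condition". Time 1 is not named as a condition.

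Section 6.0 makes the review of records part of Time 0: "Data from EHR/health records will be used to conduct a secondary eligibility screening". The next assessment described is Time 1: "This in-person assessment will include: the Repeatable Battery of Neuropsychological Status", followed by the function, mood and pain scales and a fasting blood draw. That paragraph does not mention assignment, and section 6.0 nowhere mentions randomization.

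Section 2.0, Objective 2, compares the two conditions on improvement in RBANS, FSQ, CAIDE risk score, HbA1c, metabolic panels and Roland-Morris pain.

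At Time 2, section 6.0 puts Form B of the RBANS at the same assessment as a discussion of the program: "The research team will complete qualitative interviews with participants to collect information about barriers and facilitators to completing the program". It does not say which comes first or who gives the test.

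**The concern.** Participants cannot be blind to the program they attend, and the only blinding mentioned is that of a physician to the identity of non-clinic participants during the eligibility check. Two things follow if assignment is made and communicated before Time 1.

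- **Coloured baselines.** Pain, mood and function ratings, and effort on a cognitive test, may differ between people who know they have the MI-CBT program and people who know they have information only. A baseline shift in one arm then enters the change comparison as apparent effect.
- **Missing baselines.** Someone unhappy with the assignment can leave before Time 1. That person has been randomized but has no RBANS or Roland-Morris baseline, and such losses need not be equal in the two arms.

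The first affects Objective 2. The second also touches Objective 1, because retention is one of its hypotheses. At Time 2 a related route is open: an interview about the program held before the RBANS can reveal the condition to whoever then gives the test.

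**Working it through.** **Order of steps.** The protocol states no figure to reproduce here, so the check sets the sections side by side.

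| Step | Source | Relation to assignment |
|---|---|---|
| Telephone MoCA, FSQ sections 1 and 4, memory complaint scale, 0-10 pain | 6.0 Screening phone call; 12.0 Preliminary screen | Before |
| Consent | 6.0; 12.0 | Before |
| Record review for eligibility (Time 0) | 6.0 | Before; completes the trigger |
| Random assignment | 12.0 Recruitment call | Follows the final eligibility review |
| RBANS Form A, full FSQ, pain and mood scales, blood draw (Time 1) | 6.0 | Not stated |
| Program | 5.0; 6.0 | After |

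The stated trigger is complete at Time 0. A coordinator following section 12.0 could assign at that point without breaching any sentence of the protocol. In the section 8.0 timetable, Time 0 stands in month 1 of Year 2 for the first wave, Time 1 in months 2-3 and the intervention in months 3-4, so there can be weeks between trigger and baseline.

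**Which outcomes are exposed.** No screening measure or existing record is listed as supplying a baseline RBANS or Roland-Morris score; both first appear at Time 1. Part of the FSQ and a 0-10 pain rating are taken at screening, and screening data are linked to study data, so those are safe. CAIDE components and HbA1c may be available from Time 0 records. Laboratory values are also less open to expectation than self-report.

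**Retention allowance.** The 90% hypothesis is in section 2.0 and the enrolment limits of 60 and 40 are in section 11.0.

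- 60 enrolled: 60 × 0.90 = 54 retained, so 60 − 54 = 6 losses are allowed.
- 40 enrolled: 40 × 0.90 = 36, so 4 losses.
- If the target is read for the KNA arm alone, at 30: 30 × 0.90 = 27, so 3 losses.

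Under section 13.0, leaving before completion is premature discontinuation. Each departure between assignment and Time 1 therefore uses one of these places, if the denominator is everyone randomized.

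**Possible bias in change scores.** The protocol gives no figure. Suppose allocation knowledge moves one arm's mean baseline by δ SD and leaves the post score alone.

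- Unadjusted change: false difference = δ. With δ = 0.2 (assumed), 0.2 SD.
- Baseline-adjusted comparison with slope b: false difference = b × δ. For b between 0 and 1 this runs from 0 to 0.2 SD; at b = 0.5 it is 0.1 SD.

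As a yardstick, the 95% half-width for a difference in means at 30 per arm is t(0.975, 58) × √(2/30) = 2.002 × 0.258 = 0.517 SD of the analysed score. For change scores that SD is √(2(1 − r)) baseline SDs, so the two scales agree only when the pre-post correlation r is 0.5. No significance test is planned, so the half-width only gives a sense of scale.

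**The case against.** The strongest reply is that the protocol never says Time 1 follows assignment. That is correct. Section 12.0 does not mention Time 1 and section 6.0 does not mention randomization. The sponsor may intend Time 1 first, or may withhold the assignment until the first session. There is even a weak pointer that way: section 9.0 selects the pain subsample on the Roland-Morris scale, which is not listed before Time 1. Screening has its own 0-10 pain rating, though, so selection need not wait for Time 1. None of this supplies the missing condition.

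Three stronger readings are tempting, and the document does not support them.

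- **The timetable proves assignment comes first.** A reader might take "Baseline phone assessments: groups 1&2 (T1" to mean that the arms are already formed. But the Time 0 row has the same label, "Pre-intervention EHR data extraction (groups 1&2; T0", and the review at that step precedes assignment. The label may simply mean start-date cohorts. The timetable is also out of step with the body: it shows four groups where three start dates and two conditions imply six, and telephone baselines where section 6.0 says in person.
- **Group leaders' calls push the baseline after allocation.** Section 12.0 says "The group leaders and study coordinators will call potential participants to provide more information about the respective programs". Those calls come before assignment and are shared with coordinators, so they cannot cause a late baseline. Nothing says that group leaders hold or release the allocation.
- **All baseline data are compromised.** Screening measures and Time 0 records are collected before assignment.

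It is also fair to say that attendance, acceptability and week-6 ketones, all under Objective 1, need no Time 1 baseline. For Time 2, the protocol does not say that the interviewer gives the RBANS; the point is only that order and tester are left open.

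**Conclusion.** The point holds in a limited form. Section 12.0 ties assignment to an event that is complete at Time 0, and no section makes Time 1 a condition. On the natural reading, the RBANS, Roland-Morris and other Time 1 self-report baselines for Objective 2 can be taken after allocation is known, and randomized people can be left without them.

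This rests on two assumptions: that assignment follows promptly on the review, as the wording suggests, and that participants are told when it is made. If either fails, the risk shrinks and only an unclear sentence remains. The 0.2 SD figure is illustrative and applies one for one only to unadjusted change. The retention arithmetic is firmer, but depends on a denominator that the protocol does not state.

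This is a worthwhile correction and no fatal flaw. It should be made before assignment begins, because a baseline taken after allocation cannot be replaced later.

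**What to change.** - **Section 12.0, Recruitment call:** state that participants are randomly assigned only after eligibility is confirmed and Time 1 has been completed for their start date, and that the assignment is released by a study coordinator who does not lead a group.
- **Section 6.0, Time 1:** add a matching sentence that this assessment precedes assignment.
- **Section 6.0, Time 2:** give the RBANS before the qualitative interview, by an existing team member who does not lead a group.

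If the sponsor already intends this order, the first two changes only put it in writing. Otherwise existing steps are reordered with existing staff: section 12.0 names coordinators and section 6.0 a research assistant. The cost is a shorter interval between assignment and the first session, some scheduling effort to finish Time 1 before each start date, and the $30 Time 1 payment for anyone who completes it and then leaves before assignment. Those departures become losses before randomization and should be reported as such, since they are themselves feasibility information.
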